This is a randomized, double-blind, placebo-controlled, parallel, multicenter, interventional Phase 2 study in participants aged 18 to 75 (inclusive) with active LN. The total duration of the original study was up to 68 weeks: a ≤8-week screening period (rescreening is permitted once per participant), a 48-week double-blind treatment period, and a 12-week safety follow-up period after the last dose (8 weeks after the final efficacy visit). Participants starting mycophenolate mofetil (MMF)/mycophenolic acid (MPA) at/or within 2 weeks of screening may extend screening for up to 4 additional weeks.

Unscheduled visits are permitted for reasons such as safety events or worsening of LN.

The original study design included a target of approximately 60 participants to be randomly assigned with approximately 30 participants planned per intervention group. Due to the sponsor's decision to stop screening of new participants as a result of enrollment challenges, fewer than 60 participants will be enrolled in the study. After all enrolled participants have completed the Week 20 visit, no additional study intervention will be administered. For further details, see End of Study Section of this synopsis.

A placebo comparator (in addition to standard-of-care background therapy) will be used in this study through Week 48 to allow for blinded, placebo-controlled evaluation of the long-term efficacy and safety of guselkumab in participants with LN. Participants will be stratified by geographic region and UPCR level.

Efficacy, safety, PK, immunogenicity, and biomarkers (where local regulations permit) will be assessed according to the Schedule of Activities. An optional pharmacogenomic blood sample will be collected from participants who consent to the collection of these samples (where local regulations permit).

The primary efficacy analysis will be performed after all participants have completed Week 24 efficacy assessments (or discontinued). Additional secondary endpoints will be completed at Week 24 and Week 52.

Every reasonable effort should be made to keep concomitant medications stable as defined in the protocol. Beginning at the screening visit, all concomitant therapies and all changes in concomitant therapies should be recorded throughout the study. Participants who experience an LN flare during the main study will be discontinued from study intervention.

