- c. For participants who discontinue study intervention administrations, every effort should be made to conduct final efficacy and safety assessments. Participants who permanently discontinue study intervention, but do not withdraw from study participation, should be followed at all subsequent study visits through Week 60. Week 52 may serve as the final safety follow-up visit if study medication was stopped on or before Week 40, but a full physical exam should be performed at that visit (Week 52). Sites will be notified after all enrolled participants have completed the Week 20 visit or discontinued study intervention prior to Week 24. Participants who are receiving study intervention will then complete a final efficacy visit approximately 4 weeks after the last administration of study intervention and the final safety follow-up visit approximately 12 weeks after the last administration of study intervention.
 - d. Participants who discontinue study intervention administrations and do not wish to continue in the study should return 12 weeks after the last study intervention administration for a final safety follow-up visit and complete assessment as indicated for Week 60.
 - e. Chemistry, hematology, and UPCR (x2) must be completed after the participant has received at least 8 weeks of MMF/MPA.
 - f. Refer to [Table 2](#) for additional Week 52 assessments to be performed for participants who continue in the long-term extension (LTE).
 - g. These assessments will be performed for participants who complete their Week 52 visit, but do not enter the LTE.
 - h. Urinalysis assessments should not be done within 48 hours after biopsy to limit possible blood from biopsy in urine.

Table 2: Schedule of Activities – Long-term Extension for Eligible Participants (through Week 104)																	
Week	52 ^a	56	60	64	68	72	76	80	84	88	92	96	100	104	Final Efficacy Visit ^b	Final Safety Follow-up Visit ^c	Notes
Study Procedure^d																	
Visit Window	± 7 days																
Administrative																	
Informed consent	X																Confirm participant consented to participate in LTE
Provide/Collect and review participant diary card			X		X		X		X		X		X				For participant/caregiver who is administering study intervention at home. Training should be provided at Week 60 or initial dispensation.
Study Intervention Administration																	

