5.3.2.6. Supplementary Estimand 5 (Composite)

a. **Study intervention:**

- Guselkumab (experimental treatment/intervention) in addition to standard-of-care
- Placebo in addition to standard-of-care

b. **Population:** Participants between 18 and 75 with active LN (defined by meeting the classification criteria for SLE by the 2019 European League Against Rheumatism (EULAR)/ACR, having a Class III or IV predominant kidney biopsy documentation of

ISN/RPS proliferative nephritis within the last 6 months prior to or during screening despite receiving one or more standard-of-care treatments.

- c. **Variable:** Responder binary variable, defined as a participant achieving at least 50% decrease in proteinuria from baseline at Week 24 who does not:
- discontinue study intervention for any reason excluding COVID-19 related discontinuations or
 - meet the Medication Intercurrent Event in Section (e) below
- d. **Summary measure (Population-level summary):** Difference in proportion between the study interventions
- e. **Intercurrent events and their corresponding strategies:**

Intercurrent Events	Strategy for Addressing Intercurrent Events and Its Description
Discontinuation (DC) of study intervention for any reason excluding COVID-19 related discontinuations	Composite Strategy: A participant with this intercurrent event is considered to not have achieved at least 50% decrease in proteinuria after this event, the occurrence of this intercurrent event being captured in the variable definition.
Medication Intercurrent Event 
 1. Exceeding baseline glucocorticoid dose 2. Increase above 10 mg/d prednisone equivalent after Week 12, use of new or increased dose of concomitant medication related to LN or other immunosuppressive agents 3. Initiation of prohibited medications at any time prior to the endpoint 
Note: adjustments in glucocorticoids are permitted up to and including Week 12. Nonsystemic glucocorticoids, NSAIDs, antimalarials and topical agents will not be considered an intercurrent event.
	Composite Strategy: Same as above

4. **Difference from Primary Estimand:** The first Medication Intercurrent Event, “Increase above 10 mg/d prednisone equivalent, use of new or increased dose of concomitant medication related to LN or other immunosuppressive agents” can occur at any time after Week 12, not just within 8 weeks prior to the endpoint.

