5.4. Secondary Endpoint(s) Analysis

Early Termination Note: Due to the Sponsor’s decision to stop screening of new participants as a result of enrollment challenges, fewer than 60 participants will be enrolled in the study. The end of study will occur after all enrolled participants have completed the Week 20 visit or discontinued study intervention prior to Week 24, and all participants have completed their final efficacy and safety visits per the SoA.

For secondary endpoints in the CSR, only analysis of the main estimand for each secondary endpoint that is listed below will be performed using the analysis methods specified in Sections 5.4.2.3.1 and 5.4.2.3.2:

- Proportion of participants achieving complete renal response (CRR) at Week 24 (Section 5.4.2.2.1)
- Proportion of participants achieving a sustained reduction in steroid dose ≤ 10 mg/day of prednisone or equivalent from Week 16 to Week 24 (Section 5.4.2.2.2.1)
- Proportion of participants achieving at least 50% decrease in proteinuria from baseline at Week 52 (Section 5.4.2.2.3.1)
- Proportion of participants achieving CRR at Week 52 (Section 5.4.2.2.4.1)
- Proportion of participants with UPCR < 0.5 mg/mg at Week 24 (Section 5.4.2.2.5)
- Proportion of participants with UPCR < 0.75 mg/mg at Week 24 (Section 5.4.2.2.6)
- Time to achievement of CRR (Section 5.4.2.2.7.1)
- Time to treatment failure (TF) (Section 5.4.2.2.8)

The analysis population will be the FAS except for the endpoints at Week 52, for which the FASC52 analysis set will be used.

All other analyses that are described in this section will not be performed for the CSR.

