5.4.2.1.5. Time to Treatment Failure (TF)

Time to TF is defined as time to the first occurrence of TF from baseline. TF is defined as the intercurrent events for the Supplementary Composite Estimand 5 of the primary endpoint in Section 5.3.2.6.

5.4.2.2. Estimand(s)**5.4.2.2.1. Proportion of Participants Achieving Complete Renal Response (CRR) at Week 24****Composite Estimand****1. Study intervention:**

- Guselkumab (experimental treatment/intervention) in addition to standard-of-care
- Placebo in addition to standard-of-care

2. Population: Participants between 18 and 75 with active LN (defined by meeting the classification criteria for SLE by the 2019 European League Against Rheumatism (EULAR)/ACR, having a Class III-IV kidney biopsy documentation of ISN/RPS proliferative nephritis within the last 6 months prior to or during screening despite receiving one or more standard-of-care treatments.

3. Variable: Responder binary variable, defined as a participant achieving Complete Renal Response (CRR) at Week 24 who does not:

- discontinue study intervention for any reason excluding COVID-19 related discontinuations or
- meet the Medication Intercurrent Event in Section (5) below

4. Summary measure (Population-level summary): Difference in proportion between the study interventions

5. Intercurrent events and their corresponding strategies:

Intercurrent Events	Strategy for Addressing Intercurrent Events and Its Description
Discontinuation (DC) of study intervention for any reason excluding COVID-19 related discontinuations	Composite Strategy: A participant with this intercurrent event is considered to not have achieved CRR after this event, the occurrence of this intercurrent event being captured in the variable definition.
Medication Intercurrent Event 
 1. Exceeding baseline glucocorticoid dose 2. Increase above 10 mg/d prednisone equivalent after Week 12, use of new or increased dose of concomitant medication related to LN or other immunosuppressive agents, within 8 weeks prior to the endpoint 3. Initiation of prohibited medications at any time prior to the endpoint 
Note: adjustments in glucocorticoids are permitted up to and including Week 12. Nonsystemic glucocorticoids, NSAIDs, antimalarials and topical agents will not be considered an intercurrent event.
	Composite Strategy: Same as above

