5.4.2.2.8. Time to treatment failure (TF)

Treatment Policy Estimand

1. Study intervention:

- Guselkumab (experimental treatment/intervention) in addition to standard-of-care
- Placebo in addition to standard-of-care

2. Population: Participants between 18 and 75 with active LN (defined by meeting the classification criteria for SLE by the 2019 European League Against Rheumatism (EULAR)/ACR, having a Class III-IV kidney biopsy documentation of ISN/RPS proliferative nephritis within the last 6 months prior to or during screening despite receiving one or more standard-of-care treatments.

3. Variable: Time to TF

4. Summary measure (Population-level summary): Hazard ratio of the guselkumab intervention group vs. the placebo intervention group

5. Intercurrent events and their corresponding strategies:

Intercurrent Events	Strategy for Addressing Intercurrent Events and Its Description
No intercurrent events for this endpoint	NA

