5.4.2.3.2. Time to Event Endpoints (Secondary Endpoints 7-8)

Analyses for time to event endpoints will be based upon the estimands in Section 5.4.2.2.7 through Section 5.4.2.2.8.

The hazard ratio will be estimated using the Cox proportional hazards model, adjusting for region, baseline UPCR level (<3 mg/mg and ≥ 3 mg/mg), and its 80% CI will be calculated. The proportional hazards assumption will be verified with appropriate methods (e.g. log-minus-log plots) as part of the analysis. The reported p-values for time to first flare analyses will be derived from a log-rank test. The survival curves will be estimated using Kaplan-Meier estimates.

In general, point estimates and 80% CIs for comparison between treatment groups will be reported.

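### Time to treatment failure: as written, the sponsor's stop of dosing can count as a failure, and neither a censoring rule nor a single time horizon is set

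*SAP*

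**What the plan says.** SAP 5.4 lists time to treatment failure (TF) among the secondary endpoints to be analysed for the CSR. On the analysis set it says: "The analysis population will be the FAS except for the endpoints at Week 52". Time to TF is not tied to Week 52, so it is analysed on the full analysis set.

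SAP 5.4.2.1.5 sets the event: "TF is defined as the intercurrent events for the Supplementary Composite Estimand 5 of the primary endpoint in Section 5.3.2.6". The first of those intercurrent events in SAP 5.3.2.6 is "Discontinuation (DC) of study intervention for any reason excluding COVID-19 related discontinuations". The others concern medication.

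The estimand table in SAP 5.4.2.2.8 has one entry: "No intercurrent events for this endpoint". SAP 5.4.2.3.2 gives the model: "The hazard ratio will be estimated using the Cox proportional hazards model, adjusting for region, baseline UPCR level". It adds Kaplan-Meier curves and a log-rank test, but no censoring rule.

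The Protocol synopsis describes the termination: "After all enrolled participants have completed the Week 20 visit, no additional study intervention will be administered". Footnote c of Table 1 in Protocol 1.3 expects some participants to be on treatment at that time: "Participants who are receiving study intervention will then complete a final efficacy visit approximately 4 weeks after the last administration of study intervention".

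**The concern.** TF is meant to record that therapy failed. If the sponsor's stop is a discontinuation under SAP 5.3.2.6, the TF time of a participant who was doing well on treatment records only how long before the last entrant that participant enrolled. Such events occur in both arms regardless of treatment. They dilute the hazard ratio and cost power.

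Two programmers following the text in good faith could report different hazard ratios. If the choice is made after unblinding, it becomes data-dependent.

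**Working it through.** **1. Does any rule classify the stop?**

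- *Towards an event.* SAP 5.3.2.6 excludes only COVID-19 related discontinuations. Protocol 7.1, whose subject is discontinuation of study intervention, states that study drug is withdrawn from all participants, including those in the long-term extension (LTE), if the sponsor ends development.
- *Towards a non-event.* The early-termination note in SAP 5.4 lists two alternatives: "all enrolled participants have completed the Week 20 visit or discontinued study intervention prior to Week 24". Footnote c of Table 1 describes participants at notification as still receiving treatment. The LTE schedules (Protocol Table 2 footnote b, Table 3 footnote a) list discontinuation and site notification of termination as separate triggers for the final efficacy visit.

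The non-event passages govern visit timing or the end of study. None is a TF or censoring rule.

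**2. Which horizon applies?** SAP 5.4.2.1.5, 5.4.2.2.8 and 5.4.2.3.2 state none. The candidates elsewhere are:

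| Source | Horizon |
|---|---|
| SAP 5.3.2.6, variable of the estimand supplying the events | Week 24 |
| Protocol 6.5 and Table 6 footnote b, medication-related TF | Week 52 |
| SAP 5.1, general window | Week 60 |
| SAP 1, all data pooled | End of study, including LTE |

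Time to complete renal response, by contrast, carries Weeks 24 and 52 in its heading (SAP 5.4.2.2.7).

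**3. Who is exposed?** When the last entrant reaches Week 20, someone who enrolled x weeks earlier is at Week 20 + x. The stop falls within a Week 24 horizon if x ≤ 4. It falls before the last main-study dose (Week 48) if x < 28. With N participants entering evenly over A weeks, the exposed number, before removing earlier failures, is roughly 1 + (N − 1) × 4/A or 1 + (N − 1) × 28/A. For an assumed N = 30:

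- A = 60: 1 + 29 × 4/60 = 2.9 (Week 24); 1 + 29 × 28/60 = 14.5 (Week 52).
- A = 100: 1 + 29 × 4/100 = 2.2 (Week 24); 1 + 29 × 28/100 = 9.1 (Week 52).

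Participants who finished the Week 48 dose and did not enter the LTE are not exposed. An entry period of 60 weeks or more is plausible. SAP 5.9 dates the first interim evaluation 28 December 2021 and plans it 2 months before the first LTE entry (Week 52), which puts first dosing near early 2021. Amendment 3 (29 March 2022) still aimed to improve enrolment.

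**4. What does it do to the hazard ratio?** The documents give no sample size, event rate or hazard ratio for this endpoint, so there is no figure to reproduce. Everything below is assumed: exponential TF times, true hazard ratio 0.50, a one-covariate Cox model, and a log-rank test at 1-sided 10%. First, N = 30 with 100-week entry and 1,000 runs per row. Arrows run from stop censored to stop counted as TF:

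| Horizon | Placebo TF by Week 52 | Median HR | Mean events | Power |
|---|---|---|---|---|
| Week 24 | 30% | 0.48 → 0.63 | 3.4 → 5.4 | 29.2% → 24.7% |
| Week 24 | 50% | 0.48 → 0.59 | 6.3 → 8.1 | 32.8% → 28.4% |
| Week 52 | 30% | 0.48 → 0.73 | 6.4 → 14.0 | 35.4% → 22.7% |
| Week 52 | 50% | 0.48 → 0.65 | 10.5 → 17.2 | 45.1% → 33.3% |

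With N = 20 and 40 included, the power loss in this set is 1.1 to 6.8 points (Week 24) and 6.1 to 12.7 points (Week 52).

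Second, a 12-scenario grid: 15, 18 or 25 per arm; entry over 60 or 100 weeks; 20% or 40% placebo TF by Week 24.

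- *Week 24 horizon:* 1.8 to 3.8 administrative events per trial. Median HR is 0.52 to 0.67 counted against 0.47 to 0.50 censored. Power loss is about 2 to 9 points.
- *Week 52 horizon:* median HR is 0.61 to 0.77 counted against 0.48 to 0.51 censored. Power loss is 9 to 18 points, for example 53% to 42% at 18 per arm, 60 weeks and 40% TF.

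Repeat simulations widen the counted ranges to about 0.52 to 0.71 (Week 24) and 0.58 to 0.79 (Week 52), with Week 52 power losses of about 8 to 21 points. With a true ratio of 1, rejection at the Week 52 and LTE horizons is 8.5% to 11.9% counted and 8.5% to 11.7% censored.

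**The case against.** The best reply is that the event reading is the less natural one. The termination notes, footnote c and the LTE footnotes all treat the stop as something other than discontinuation. Protocol 9.4.2 describes TF through glucocorticoid or immunosuppressive use. This stands in part: the documents do not show that the sponsor intends to count these participants as failures, and a reader who infers that goes too far. But Protocol 9.4.2 leaves the definition to the SAP, and the SAP then includes discontinuation with a single exclusion.

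A reader might also infer that no horizon exists anywhere. That is too strong. Several exist, and the medication-related TF passages point to Week 52. What is missing is a horizon in the endpoint's own sections and agreement among the general ones. With Week 24 the effect is modest, so the Week 52 figures should not be read as the whole range.

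Finally, the stakes are limited. Trial success rests on the primary endpoint (SAP 3), this is one secondary endpoint in a terminated Phase 2 study, and the estimate will be imprecise either way. That stands, and it sets the weight of the point.

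**Conclusion.** The concern holds as a cheap improvement. A stated rule, applied as written, turns participants stopped by the sponsor into failures; contrary text exists but is not a rule. The direction is firm: these events carry no treatment information and move the hazard ratio towards 1. The size is illustrative, because sample size, accrual, TF rate and the true ratio of 0.50 are all assumed. The median ratio moves from about 0.5 to about 0.52 to 0.71 with a Week 24 horizon, or about 0.6 to 0.8 with a Week 52 horizon.

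Two stronger inferences are not supported. There is no inflation of false positives, since rejection under no effect stays near 10%. Nor is harm shown to other endpoints: those at Week 52 are largely protected by restricting them to participants with the opportunity to reach that visit (FASC52, SAP 4), and no effect on the primary or other Week 24 endpoints has been demonstrated.

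**What to change.** Amend SAP 5.4.2.1.5 before the single database lock:

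1. State that the sponsor's stop of dosing because of study termination is not a TF event.
2. Censor those participants administratively at their final efficacy visit, defined separately for the main study (about 4 weeks after the last dose, Table 1 footnote c) and the LTE (on site notification, Tables 2 and 3).
3. Name one horizon for this endpoint and reconcile it with SAP 1, 5.1 and 5.3.2.6 and with Protocol 6.5 and Table 6.

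The cost is a few sentences and one derivation rule. The downside is fewer counted events and a wider interval. At the Week 52 horizon on the 12-scenario grid, the ratio of upper to lower 80% limit is 2.9 to 8.1 when censored, against 2.3 to 3.8 when the stop is counted. The narrower interval comes only from counting administrative events. SAP 5.2 summarises reasons for discontinuation but names only COVID-19, so confirm that sponsor termination is a recorded reason, or derive it from the site notification date.

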Antimalarials (chloroquine, hydroxychloroquine, or quinacrine)	≤ 250 mg/day chloroquine (≤ 3 mg/kg/day) ≤ 400 mg/day hydroxychloroquine ≤ 100 mg/day quinacrine	Stable dosing through Week 52. Initiation of new antimalarial treatment is not permitted through Week 52.
Oral glucocorticoids ^b	Stable oral glucocorticoids at minimum prednisone equivalent dose of 10 mg/day and maximum 1 mg/kg/day or ≤ 60 mg/day, whichever is lower.	Week 2 Through Week 12 - tapering starting from Week 2 to prednisone 5 mg equivalent PO daily by Week 12 according to schedule (Appendix 7 [Section 10.7]) Reason(s) for not tapering glucocorticoids should be documented
NSAIDs and other analgesics	Stable dosing through Week 52 with no more than the usual marketed doses approved in the country where the study is being conducted. Notable changes in NSAID dosing to be recorded in concomitant medications. The initiation of treatment with NSAIDs should be avoided unless other analgesics are contraindicated.	
Anti-hypertensive medications (ARBs or ACE inhibitors)	No more than the usual marketed doses approved in the country where the study is being conducted. The initiation of treatment with ARB or ACE inhibitors should be avoided between randomization and Week 52 unless other hypertensive treatments are contraindicated. Substitution of ACE inhibitors for ARBs or ARBs for ACE inhibitors is permitted if medically necessary.	
Non-biologic immunomodulators: MMF MPA	≤ 3 g/day ≤ 2.2 g/day	Stable dosing through Week 52. Initiation of a new immunomodulator is not permitted through Week 52.

^a Permitted concomitant medications are not supplied by the sponsor.

^b Between Weeks 12 and 52, participants requiring average daily doses of glucocorticoids for SLE or LN disease activity that exceed their baseline dose at Week 0 may be categorized as TFs. While these participants will be permitted to remain in the study, the investigator must consider whether glucocorticoid dose increases to an average daily dose ≥ 60 mg prednisone or equivalent for more than 7 consecutive days or whether a requirement for multiple rescues with glucocorticoid therapy between Weeks 12 and 52 should result in discontinuation of study intervention administration (see Section 7.1).

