9.4.2. Primary Endpoint(s)

The primary endpoint is the proportion of participants achieving at least a 50% decrease in proteinuria from baseline at Week 24.

Primary endpoint analysis

Analyses of the primary efficacy endpoint ($\geq 50\%$ decrease in proteinuria from baseline at Week 24) will include data from all randomized participants who received at least one administration of study intervention based on their assigned intervention group, regardless of the actual intervention received and have baseline data (Evaluable population).

Treatment Failure Criteria may include: initiation or increased use of a glucocorticoid or other immunosuppressive agents, however these will be further defined in the SAP.

Participants who meet any of the TF criteria defined in the SAP will be assumed a non-responder, ie, did not meet the $\geq 50\%$ decrease in proteinuria criteria at Week 24.

The primary analysis will be based on the composite estimand where participants meeting TF criteria are assumed non-achievers from the point of TF forward, and missing data are assumed as non-achievers as well.

The study will be considered a success if the 1-sided p-value from the difference in proportion of participants with $\geq 50\%$ decrease in proteinuria between the guselkumab and placebo intervention groups from a logistic MMRM longitudinal model is less than a 1-sided alpha of 10%.

See the SAP for further details about the analysis of the primary endpoint, including sensitivity and subgroup analyses.

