9.4.3. Secondary Endpoint(s)

Major secondary endpoints include:

1. Proportion of participants achieving CRR at Week 24.
2. Proportion of participants achieving a sustained reduction in steroid dose ≤ 10 mg/day of prednisone or equivalent from Week 16 to Week 24.

3. Proportion of participants achieving at least 50% decrease in proteinuria from baseline at Week 52.
4. Proportion of participants achieving CRR at Week 52.
5. Proportion of participants with UPCR <0.5 mg/mg at Week 24.
6. Proportion of participants with UPCR <0.75 mg/mg at Week 24.
7. Time to CRR.
8. Time to TF.

Secondary endpoint analyses

The Evaluable population will be used for analysis and participants will be counted in the intervention group assigned, regardless of the study intervention received.

Treatment failure and missing data will be included in the secondary endpoint estimands as non-achievers or non-responders.

The details of the analysis of the major secondary endpoints will be included in the SAP.

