5.4.2.1.3. Glucocorticoid (Prednisone or Prednisone Equivalent) Reduction

1. Participants with a sustained reduction in steroid dose ≤ 10 mg/day of prednisone or equivalent are participants who sustained a continuous reduction in steroid to ≤ 10 mg/day of prednisone or equivalent for the time duration measured.

The average daily dose for any given day is the average of the last available (non-missing) values within 7 days, including the day of interest.

2. Reduction of glucocorticoid dose is defined as:
 - A reduction in average daily oral glucocorticoid dose down to ≤ 10 mg/day by Week 12
 - and
 - at least a 50% decrease from baseline dose.
3. Other considerations to meet sustained reduction of glucocorticoid dose include

Dose adjustments after starting reduction of glucocorticoid dose are permitted and participants will still be considered to have sustained reduction unless they return to or exceed their baseline (Week 0) dose. These dose adjustments are permitted up to the Week 12 visit only.

Note: 10 mg of prednisone equivalent is used here although the tapering target is 5 mg. Dose increases above 10 mg of prednisone equivalent or above 50% of baseline dose after Week 12 will not be considered as sustained reduction in glucocorticoids.

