5.4.2.2.2. Proportion of Participants Achieving a Sustained Reduction in Steroid Dose ≤ 10 mg/day of Prednisone or Equivalent from Week 16 to Week 24

5.4.2.2.2.1. Main Estimand (Composite)

1. Study intervention:

- Guselkumab (experimental treatment/intervention) in addition to standard-of-care
- Placebo in addition to standard-of-care

2. Population: Participants between 18 and 75 with active LN (defined by meeting the classification criteria for SLE by the 2019 European League Against Rheumatism (EULAR)/ACR, having a Class III-IV kidney biopsy documentation of ISN/RPS proliferative nephritis within the last 6 months prior to or during screening despite receiving one or more standard-of-care treatments.

3. Variable: Responder binary variable, defined as a participant achieving a sustained reduction in steroid dose ≤ 10 mg/day of prednisone or equivalent from Week 16 to Week 24

4. Summary measure (Population-level summary): Difference in proportion between the study interventions

5. Intercurrent events and their corresponding strategies:

Intercurrent Events	Strategy for Addressing Intercurrent Events and Its Description
Discontinuation (DC) of study intervention for any reason excluding COVID-19 related discontinuations	Composite Strategy: A participant with this intercurrent event is considered to not have achieved Sustained Reduction in Steroid Dose after this event, the occurrence of this intercurrent event being captured in the variable definition.
Medication Intercurrent Event 1. Initiation of prohibited medications at any time prior to the endpoint Note: Nonsystemic glucocorticoids, NSAIDs, antimalarials and topical agents will not be considered an intercurrent event.	Composite Strategy: Same as above

5.4.2.2.2.2. Supplementary Estimand (Treatment Policy (de Facto))

All attributes (1-4) of the supplementary estimand are the same as above main estimand (Section 5.4.2.2.2.1) except for the intercurrent events, where a treatment policy strategy is used instead.

5. Intercurrent events and their corresponding strategies:

Intercurrent Events	Strategy for Addressing Intercurrent Events and Its Description
Discontinuation (DC) of study intervention for any reason excluding COVID-19 related discontinuations	Treatment Policy Strategy: The intercurrent event addressed with a treatment policy strategy, targeting the effect of the assignment to the treatment group, regardless of the occurrence of the intercurrent events.

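### The main estimand for sustained steroid reduction omits new or increased LN or immunosuppressive medication as an intercurrent event, so a participant whose permitted background therapy is raised can count as an achiever

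*SAP*

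**What the plan says.** Secondary Endpoint 2 is sustained steroid reduction from Week 16 to Week 24. SAP 5.4.2.1.3 describes achievers as participants "who sustained a continuous reduction in steroid to ≤ 10 mg/day of prednisone or equivalent for the time duration measured". The definition concerns glucocorticoid dose only.

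The main estimand in SAP 5.4.2.2.2.1 handles two intercurrent events with the composite strategy: "Discontinuation (DC) of study intervention for any reason excluding COVID-19 related discontinuations" and "Initiation of prohibited medications at any time prior to the endpoint". SAP 5.4 keeps only this main estimand for the study report, so the treatment-policy supplementary estimand will not be run.

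Protocol 9.4.3 states: "Treatment failure and missing data will be included in the secondary endpoint estimands as non-achievers or non-responders". Protocol 9.4.2 leaves the criteria to the SAP but indicates their scope: "Treatment Failure Criteria may include: initiation or increased use of a glucocorticoid or other immunosuppressive agents". SAP 5.4.2.1.5 then fixes the definition: "TF is defined as the intercurrent events for the Supplementary Composite Estimand 5 of the primary endpoint". Those events, in SAP 5.3.2.6, include "use of new or increased dose of concomitant medication related to LN or other immunosuppressive agents".

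For MMF/MPA during the blinded period, Protocol Table 6 requires: "Stable dosing through Week 52. Initiation of a new immunomodulator is not permitted through Week 52". SAP Appendix 2, which records changes to protocol-planned analyses, reads N/A.

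**The concern.** The two glucocorticoid triggers used in the other estimands can reasonably be left out here, because steroid dose is itself the outcome. The non-steroid half of the same item went with them, and the outcome does not capture that half. Raising a background immunosuppressant is a plausible alternative to raising steroids. If such a participant counts as an achiever, a difference between arms on this endpoint mixes steroid reduction with substitution by other therapy. The same report would also class that participant as a treatment failure in the time-to-TF analysis, with no explanation of why the two analyses differ.

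**Working it through.** **Step 1. Compare the main estimands of the six binary secondary endpoints.**

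| Endpoint | SAP section | Is new or increased LN or immunosuppressive medication an event? |
|---|---|---|
| 1. CRR, Week 24 | 5.4.2.2.1 | Yes, in the 8 weeks before the endpoint |
| 2. Sustained steroid reduction | 5.4.2.2.2.1 | No |
| 3. 50% proteinuria decrease, Week 52 | 5.4.2.2.3.1 | Yes, same window |
| 4. CRR, Week 52 | 5.4.2.2.4.1 | Yes, same window |
| 5. UPCR <0.5, Week 24 | 5.4.2.2.5 | Yes, same window |
| 6. UPCR <0.75, Week 24 | 5.4.2.2.6 | Yes, same window |

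**Step 2. Follow one participant through the rules.** Suppose the participant stays on study intervention, meets the glucocorticoid conditions of SAP 5.4.2.1.3, and has MMF raised between Weeks 16 and 24.

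- *Discontinuation event:* not triggered, since study intervention continues.
- *Prohibited-medication event:* not triggered. Protocol 6.5.7 prohibits additional immunosuppressants other than those the eligibility criteria allow. Inclusion criterion 5 allows MMF up to 3 g/day and MPA up to 2.2 g/day. An increase breaches the stable-dose requirement of Table 6 but does not start a prohibited drug.
- *Result for Endpoint 2:* achiever.
- *Result for the primary endpoint and for CRR at Week 24:* non-responder.
- *Result for time to TF:* treatment failure.

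**Step 3. Check whether other provisions close the gap.**

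- Protocol 4.1.1 and 6.5 require discontinuation when an LN flare needs an immunomodulator change beyond what is permitted. Endpoint 2 counts that as failure.
- New immunosuppressants are mostly on the prohibited list in 6.5.7, so they are counted too.
- Some increases remain. Protocol 6.5 asks investigators to consider whether increased background therapy warrants discontinuation. Protocol 6.5.8 asks for discussion with the medical monitor. Protocol 7.1 lists persistent inadequate response only among the conditions for considering discontinuation. Participants who continue after such an increase are the ones missed.

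**Step 4. Check the Variable attribute.** The strategy column of 5.4.2.2.2.1 says the event is captured in the variable definition. The Variable attribute there carries no exclusion clause, whereas the one for CRR at Week 24 does. The section is incomplete even for the two events it lists.

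**Step 5. Scale.** One participant changes an arm's proportion by 100/n points. The original target was about 30 per arm, and fewer than 60 in total will now be enrolled. The smaller arm sizes are assumptions.

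- n = 30: 100/30 = 3.3 points
- n = 20: 100/20 = 5.0 points
- n = 15: 100/15 = 6.7 points
- n = 10: 100/10 = 10.0 points

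**The case against.** The best defence is that the list was tailored on purpose. The note on glucocorticoid adjustments was also removed for this endpoint, and the supplementary estimand repeats the shortened list. Neither document says the endpoint is meant to show steroid reduction on unchanged background therapy. Protocol Section 9 is labelled the original plan, given for information, and leaves secondary-endpoint detail to the SAP. It is therefore too strong to read the SAP as breaking a binding protocol rule. What stands is that the SAP's own treatment-failure definition contains the event, five parallel estimands keep it, and no reason is recorded. Protocol 6.5, which does not carry the original-plan label, also says that non-compliant changes in concomitant therapy may make a participant a TF for primary and secondary endpoints through Week 52.

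A second defence is that being a TF in one analysis and a responder in another is not peculiar to this endpoint. This is correct. The TF definition has no 8-week limit, so an increase that ended before Week 16 can be a TF event and still leave the participant a responder on the primary endpoint. The point therefore rests on the event being absent altogether, not on that overlap.

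A third defence is that this is one of eight secondary endpoints, without multiplicity control, in a terminated Phase 2 study, and that time to TF will show these escalations anyway. This lowers the priority, but it does not make the achiever classification right.

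**Conclusion.** The omission is real and should be corrected, within limits. It affects participants who remain on study intervention and at or below 10 mg/day while permitted background LN therapy is increased.

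A reader might infer that every escalated participant is counted as a success. The discontinuation and prohibited-medication events rule that out.

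A reader might also infer that the placebo rate is inflated and a true effect hidden. For example, 3 of 30 escalated on placebo against 1 of 30 on guselkumab would give (3 − 1)/30 = 6.7 points. Those counts would be invented: the documents give no escalation rate, no steroid-response rate and no split by arm. Neither the size nor the direction of any bias can be established, and the per-participant figures indicate scale only.

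The conclusion assumes that raising a permitted drug is not read as starting a prohibited one. The wording of the event and of Protocol 6.5.7 supports that reading.

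**What to change.** Before database lock, make these changes in SAP 5.4.2.2.2.1:

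- Add to the Medication Intercurrent Event, with the composite strategy, the non-steroid part of item 2 (new or increased LN-related or immunosuppressive medication). Use the wording and window of the other Week 24 secondary estimands: 24 − 8 = 16, so Weeks 16 to 24, which is also the endpoint's own measurement period. A window from first dose would be stricter than those estimands and would create a new mismatch.
- Leave the glucocorticoid triggers out, since the outcome captures them.
- Add to the Variable attribute the exclusion of participants who have an intercurrent event, as in SAP 5.4.2.2.1.
- State whether ACE-inhibitor or ARB changes that Protocol 6.5.4 permits count as LN-related medication, and whether continued use in the window of a dose raised earlier counts.

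If the shorter list is intended, record it in SAP Appendix 2 with the reason.

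The cost is a few lines of text. Concomitant therapy changes are already recorded throughout the study, so no new data are needed. The achievement rate may be slightly lower. The change concerns only how outcomes are classified and takes no view on how background therapy should be managed.
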